- ^c Patients with confirmed PD who continue to receive the study drug at the discretion of the Investigator (following consultation with AstraZeneca) can receive the study drug for a maximum of 24 months from Cycle 1 Day 1. For all patients who are treated through progression, the Investigator should ensure patients do not have any significant, unacceptable, or irreversible toxicities that indicate continuing treatment will not further benefit the patient. The patient must continue to meet those inclusion and exclusion criteria that are relevant to treatment through disease progression as specified in [Section 6.1.3](#). The same exceptions as noted in footnote ^b apply. Patients will follow the assessments in [Table 1](#) including tumour assessments q8w (relative to the date of IP treatment initiation) until the study drug is stopped. Patients who continue to receive treatment after the DCO should receive tumour assessment scans and other assessments as per local clinical practice. It is recommended that the patients continue the scheduled site visits and Investigators monitor the patient's safety laboratory assessments prior to and periodically during the treatment with durvalumab (MEDI4736) in order to manage AEs in accordance with the durvalumab (MEDI4736) toxicity management guidelines ([Section 8.4.5](#)). The study drug should be discontinued if there is confirmed PD in TLs following a previous response (PR or CR) to the study drug in those lesions.

Note: At DCO for the study, patients who are receiving IP can either choose to discontinue from the study or, where the Investigator judges that patients are gaining clinical benefit, patients may continue to receive IP. For patients who do continue to receive IP beyond the time of the DCO, Investigators must continue to report all SAEs to AstraZeneca Patient Safety until 90 days after last IP dose. Any SAE or non-serious AE ongoing at the time of the DCO is to be followed up at the discretion of the Investigator and per local practice and in alignment with the Dosing Modification and Toxicity Management Guidelines ([Section 8.4.5](#)), unless the event is considered by the Investigator to be unlikely to resolve or the patient is lost to follow-up.

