6.1.2 Dose and treatment regimens

Patients will receive 1500 mg durvalumab (MEDI4736) monotherapy via IV infusion q4w for up to a maximum of 24 months from Cycle 1 Day 1 (up to 26 doses/cycles) with the last administration at Week 104 (Figure 3). The study drug should be discontinued prior to 24 months if there is clinical progression or confirmed radiological progression or if there is unacceptable toxicity, withdrawal of consent, or another discontinuation criterion is met. Please note, if a patient's weight decreases to ≤ 30 kg, the patient should receive weight-based dosing equivalent to 20 mg/kg of durvalumab (MEDI4736) q4w after consultation between the Investigator and Study Physician, until the weight improves to >30 kg, at which point the patient should start receiving the fixed dosing of durvalumab (MEDI4736) 1500 mg q4w.

Figure 3 Durvalumab (MEDI4736) monotherapy dosing schedule

^a Or until discontinuation of study drug due to any of the reasons listed in Section 7.1.

Max.: Maximum; PD: Progression of disease; q4w: Every 4 weeks.

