6.1.3 Duration of treatment and criteria for treatment through progression and discontinuation

Patients with CR, PR, or SD (based on Investigator assessment) following completion of sCRT will receive durvalumab (MEDI4736) treatment for a maximum of 24 months or until RECIST 1.1-defined PD (unless the Investigator considers the patient continues to receive benefit from the IP), initiation of alternative cancer therapy, unacceptable toxicity, withdrawal of consent, or another discontinuation criterion is met.

During the treatment period, patients who are clinically stable at an initial RECIST 1.1-defined PD may continue to receive the study drug at the discretion of the Investigator and patient, as long as they are deemed to be receiving clinical benefit, after re-consenting for treatment through progression. For all patients who are treated through progression, the Investigator should ensure that:

- The patient does not have any significant, unacceptable, or irreversible toxicities that indicate continuing treatment will not further benefit the patient.
- There is absence of clinical symptoms or signs indicating clinically significant disease progression accompanied by a decline in WHO/ECOG PS to >1 for the Cohort of PS 0 to 1 patients, and to >2 for the Cohort of PS 2 patients.
- There is absence of rapid disease progression or threat to vital organs or critical anatomical sites (eg, central nervous system metastasis, respiratory failure due to tumour compression, or spinal cord compression) requiring urgent alternative medical intervention. (Concurrent radiation treatment is not permitted. If patients require palliative radiation or prophylactic radiation [eg, of brain], consult AstraZeneca for exception to this rule; protocol therapy will need to be held prior to and during the radiation.)
- The patient still fulfils the eligibility criteria for this study (see Sections 5.1 and 5.2) with the exception of inclusion criterion 11 and exclusion criteria 13, 16, 17, 18, and 21.
- The patient agrees to re-consenting to be treated through progression.

An individual patient will not receive any further IP if any of the discontinuation criteria listed in Section 7.1 apply.

Treatment after final overall survival data cut-off

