7 DISCONTINUATION OF TREATMENT AND SUBJECT WITHDRAWAL

7.1 Discontinuation of study drug

An individual patient will not receive any further IP if any of the following occur in the patient in question:

- Withdrawal of consent from further treatment with IP. The patient is, at any time, free to discontinue treatment, without prejudice to further treatment. Patient who discontinue treatment are normally expected to continue to participate in the study unless they specifically withdraw their consent to further participation in any study procedures and assessments (see Section 7.3).
- An AE that, in the opinion of the Investigator or AstraZeneca, contraindicates further dosing.
- Any AE that meets criteria for discontinuation as defined in the Dosing Modification and Toxicity Management Guidelines (Section 8.4.5).
- Pregnancy or intent to become pregnant.

- Non-compliance with the study protocol that, in the opinion of the Investigator or AstraZeneca, warrants withdrawal from treatment with IP (eg, refusal to adhere to scheduled visits).
- Initiation of alternative anticancer therapy including another IP.
- Clinical progression or confirmed radiological progression (refer to [Appendix F](#)) and Investigator determination that the patient is no longer benefitting from treatment with the IP.

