Patients with ‘symptomatic deterioration’ requiring discontinuation of treatment without objective radiologic evidence of disease progression at that time should continue to undergo tumour assessments where clinically feasible.

Evaluation of overall visit response

The overall visit response will be derived using the algorithm shown in [Table 17](#).

Table 17 Overall visit response

| Target lesions | Non-target lesions | New lesions | Overall response |
|----------------|--------------------|-------------|------------------|
| CR | CR | No | CR |
| CR | NA | No | CR |
| CR | Non-CR/Non-PD | No | PR |
| CR | NE | No | PR |
| PR | Non-PD or NE | No | PR |
| SD | Non-PD or NE | No | SD |
| NE | Non-PD or NE | No | NE |
| PD | Any | Yes or No | PD |
| Any | PD | Yes or No | PD |
| Any | Any | Yes | PD |

CR: Complete response; NA: Not applicable (only relevant if there were no target and/or NTLs at baseline); NE: Not evaluable; NTL: Non-target lesion; PD: Progression of disease; PR: Partial response; SD: Stable disease.

Confirmation of radiological progression

A follow-up scan is performed after the initial RECIST 1.1-defined PD, preferably at the next (and no later than the next) scheduled imaging visit, and no less than 4 weeks after the prior assessment of PD, and the Confirmation of Radiological Progression Criteria described below are applied for tumour assessments of this follow-up scan. Patients with confirmed radiological PD who continue to receive study drug at the discretion of the Investigator and patient (following consultation with AstraZeneca) can receive treatment until no longer having clinical benefit and will continue to have tumour assessments on their regular imaging schedule for the duration of treatment.

Confirmation of radiological progression guidelines are set for the following reasons:

- For patient management and treatment decisions.
- In the absence of significant clinical deterioration, to promote the collection of additional scans after the first radiologic RECIST 1.1 assessment of PD in order to distinguish pseudoprogression from true radiologic progression.

Confirmation of Radiological Progression Criteria

An immediate prior RECIST 1.1-defined radiologic PD would be considered confirmed if any of the following criteria are met in the subsequent follow-up scan (acquired preferably at the next regularly scheduled imaging visit but no sooner than 4 weeks after the RECIST 1.1-defined PD scan):

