- Exclusion Criterion 13: Patients who have received cCRT for locally-advanced NSCLC, or who received sCRT with at least 2 concomitant CRT cycles. Prior surgical resection (ie, Stage I or II) is permitted.  
  
Note: Patients whose platinum-based chemotherapy contained gemcitabine and who received sCRT with at least 1 concomitant CRT cycle are excluded from this study.
- Exclusion Criterion 16: Prior exposure to immune-mediated therapy, including but not limited to, other anti-CTLA-4, anti-PD-1, anti-PD-L1, and anti-PD-L2 antibodies, excluding therapeutic anticancer vaccines.
- Deviation 2: The patient met discontinuation criteria but did not discontinue durvalumab (eg, patient withdrew consent, patient became pregnant).
- Deviation 3: The patient received a prohibited concomitant medication or procedure as detailed in Section 6.4 of the CSP or any other concomitant medication or procedure which, upon physician review of all medications and procedures prior to database lock (DBL), is considered to have a potential effect on study outcomes.
- Deviation 4: Missed visits, assessments, or treatments that, in the opinion of the principal investigator,
  - were due to the 2020 COVID-19 global pandemic and
  - there was a significant effect on either completeness, accuracy, and/or reliability of the patient's data, or the patient's rights, safety or well-being.

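### The protocol's texts on stopping durvalumab at progression conflict: Figure 2 footnote c adds a target-lesion stop and a sponsor consultation that the governing list in Section 7.1 lacks, and Section 6.1.2 omits the benefit condition

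*Protocol*

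**What the plan says.** - **Protocol 6.1.2:** "The study drug should be discontinued prior to 24 months if there is clinical progression or confirmed radiological progression". The sentence goes on to toxicity, consent withdrawal and any other discontinuation criterion. It has no benefit exception.
- **Protocol 7.1:** names the same two kinds of progression, then adds "and Investigator determination that the patient is no longer benefitting from treatment with the IP".
- **Protocol 6.1.3:** lets clinically stable patients be treated through progression under listed conditions, and closes with "An individual patient will not receive any further IP if any of the discontinuation criteria listed in Section 7.1 apply". Figure 3 footnote a, inside 6.1.2, also points to 7.1.
- **Protocol 4.1, Figure 2 footnote c:** opens with "Patients with confirmed PD who continue to receive the study drug at the discretion of the Investigator (following consultation with AstraZeneca" and permits dosing for up to 24 months from Cycle 1 Day 1. Later it says "The study drug should be discontinued if there is confirmed PD in TLs following a previous response (PR or CR) to the study drug", limited to the lesions that had responded.
- **Protocol Appendix F, Confirmation of radiological progression:** patients with confirmed radiological PD, after consulting the sponsor, "can receive treatment until no longer having clinical benefit". Table 1 footnote b has the same consultation step.
- **Protocol synopsis, Protocol 4.1 (main text) and SAP 1.2.1:** stop at progression, except where the Investigator considers that the patient still benefits.
- **SAP 2.2.1, Deviation 2:** "The patient met discontinuation criteria but did not discontinue durvalumab". The examples are consent withdrawal and pregnancy. No protocol section is cited.

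**The concern.** These are not different levels of detail on one rule. For some patients they give opposite instructions. This is a safety study, and the instruction at issue is whether a progressing patient keeps receiving the drug. Two sites could treat the same patient differently and each point to protocol text in support.

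The SAP makes it an important protocol deviation to keep dosing a patient who has met discontinuation criteria, but does not say which text supplies those criteria. For patients dosed past confirmed progression, the classification then depends on the section consulted.

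**Working it through.** The plan states no figure on this point, so the check is a comparison of texts.

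| Text | Confirmed radiological PD, Investigator sees benefit | Separate stop for responding target lesions | Sponsor consultation before continuing |
|---|---|---|---|
| Protocol 6.1.2 | Stop | No | No |
| Protocol 7.1 | Criterion not met | No | No |
| Protocol 6.1.3 | May continue, with conditions | No | No |
| Figure 2 footnote c | May continue | Yes | Yes |
| Appendix F | May continue | No | Yes |
| Table 1 footnote b (radiological PD) | May continue | No | Yes |
| Synopsis, 4.1 main text, SAP 1.2.1 | May continue | No | No |

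**Case A.** Confirmed radiological PD, clinically stable, perceived benefit, no earlier response. Section 6.1.2 says stop. Section 7.1 is not met. Footnote c and Appendix F allow continuation after consultation. If dosing continues, Deviation 2 is met under 6.1.2 and not under 7.1.

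**Case B.** As A, but the confirmed PD is in target lesions that had responded. Section 6.1.2 and footnote c say stop. Section 7.1 is not met, and Appendix F allows continuation. If dosing continues, Deviation 2 is met under 6.1.2 and footnote c, and not under 7.1. Treating 7.1 as the only authority gives one answer, but it silently cancels the stop in footnote c.

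**Case C.** As A, but the site continues without consulting the sponsor. That satisfies 6.1.3 and 7.1 on this point and departs from footnote c, Table 1 footnote b and Appendix F.

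Section 7.1 also has an ambiguity of its own: its wording does not show whether the benefit condition qualifies clinical progression as well as confirmed radiological progression.

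**Reach into the endpoints.**

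- PFS is defined regardless of discontinuation (Protocol 9.4, SAP 3.3.1), so the stopping rule does not enter its definition.
- The primary endpoint (SAP 3.2.1) counts events to Day 183, to 90 days after discontinuation, or to subsequent therapy, whichever is earliest. Taking discontinuation as the last dose, 183 − 90 = 93. A last dose on or after Day 93 leaves the whole window open if no new therapy starts.
- On scheduled scans, confirmed PD cannot come before 8 − 1 + 4 = 11 weeks, which is Day 78. With on-time dosing (Days 1, 29, 57, 85, 113), a last dose on Day 57 closes the window at 57 + 90 = Day 147, or 183 − 147 = 36 days early. A last dose on Day 85 closes it at Day 175, 8 days early.
- Only early progressors are therefore touched. Earlier clinical progression, a prompt start of new therapy, and events caused by extra doses are further routes that the documents do not let one size.

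**The case against.** The strongest reply is that a governing rule already exists. Section 6.1.3 makes the 7.1 list binding, Figure 3 footnote a points to it from within 6.1.2, and Table 5 footnote a sends the reader to 6.1.3 for treatment through progression. Section 6.1.2 can then be read as shorthand. Nearly every other text allows continuation on benefit, and the two examples in Deviation 2 both appear in 7.1.

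Much of this stands. On the benefit condition, 6.1.2 is close to a lone outlier, although Section 8.1 also describes treatment as running until progression without a benefit exception. The reply does not reach the target-lesion stop or the consultation step. Deferring to 7.1 removes both from force without saying so, and the Deviation 2 examples do not address progression.

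A reader might infer more than the documents support:

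- **That 6.1.2 is a mandatory stop.** Both 6.1.2 and footnote c are worded as recommendations (should). Section 7.1 is the text that says the patient will not be dosed.
- **That the deviation count cannot be interpreted.** The SAP provides for regular deviation review and final classification before database lock or data cut-off (2.2.2), and its examples match 7.1. No analysis set excludes patients for deviations (2.1), so reclassification removes nobody. Only an optional sensitivity analysis could follow.
- **That adverse-event counts change with the text read.** The treatment-emergent window runs from the actual last dose and closes earlier at subsequent therapy (SAP 3.2.3). For a given dosing history the counts are the same. They differ only if sites act differently.
- **That the PACIFIC PFS rates in Protocol 4.2.4 size the problem.** Those rates count first progressions and deaths in PS 0 to 1 patients after concurrent chemoradiation. They do not count patients dosed past confirmed progression after sequential therapy.

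**Conclusion.** The inconsistency is real and should be resolved. It has three parts: an unreconciled target-lesion stop in Figure 2 footnote c, a missing benefit condition in Section 6.1.2, and a sponsor consultation required in some texts but absent from 6.1.3 and 7.1. The first is the most substantive, because accepting 7.1 as governing does not settle what footnote c intends.

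Its size in patients is unknown. The documents give no rate of treatment past confirmed progression, and none of confirmed target-lesion progression after response among patients still on drug. The consequences fall on site conduct, patient exposure and the deviation table. PFS is not affected by definition, and the primary endpoint is affected only through early progressors. That last judgement assumes dosing and scans close to schedule. No view is taken on which stopping rule is clinically right.

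**What to change.** Reconcile Protocol 6.1.2, 6.1.3, 7.1, Figure 2 footnote c and Appendix F into one rule held in Section 7.1, with the other places cross-referring to it. The rule should state:

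1. whether the target-lesion stop after a response applies;
2. whether sponsor consultation is needed before dosing continues;
3. whether the benefit condition covers clinical progression as well as confirmed radiological progression.

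Table 1 footnote b, Section 8.1 and SAP 1.2.1 should be brought into line with the result. SAP Deviation 2 should cite Protocol 7.1 as its only source of criteria. The content of the rule is for the sponsor's clinical team.

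The cost is a protocol wording amendment and small SAP wording edits. Some patients already dosed past confirmed progression may be reclassified in the deviation table. No endpoint definition, analysis set or sample size changes.

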6.1.3 Duration of treatment and criteria for treatment through progression and discontinuation

Patients with CR, PR, or SD (based on Investigator assessment) following completion of sCRT will receive durvalumab (MEDI4736) treatment for a maximum of 24 months or until RECIST 1.1-defined PD (unless the Investigator considers the patient continues to receive benefit from the IP), initiation of alternative cancer therapy, unacceptable toxicity, withdrawal of consent, or another discontinuation criterion is met.

During the treatment period, patients who are clinically stable at an initial RECIST 1.1-defined PD may continue to receive the study drug at the discretion of the Investigator and patient, as long as they are deemed to be receiving clinical benefit, after re-consenting for treatment through progression. For all patients who are treated through progression, the Investigator should ensure that:

- The patient does not have any significant, unacceptable, or irreversible toxicities that indicate continuing treatment will not further benefit the patient.
- There is absence of clinical symptoms or signs indicating clinically significant disease progression accompanied by a decline in WHO/ECOG PS to >1 for the Cohort of PS 0 to 1 patients, and to >2 for the Cohort of PS 2 patients.
- There is absence of rapid disease progression or threat to vital organs or critical anatomical sites (eg, central nervous system metastasis, respiratory failure due to tumour compression, or spinal cord compression) requiring urgent alternative medical intervention. (Concurrent radiation treatment is not permitted. If patients require palliative radiation or prophylactic radiation [eg, of brain], consult AstraZeneca for exception to this rule; protocol therapy will need to be held prior to and during the radiation.)
- The patient still fulfils the eligibility criteria for this study (see Sections 5.1 and 5.2) with the exception of inclusion criterion 11 and exclusion criteria 13, 16, 17, 18, and 21.
- The patient agrees to re-consenting to be treated through progression.

An individual patient will not receive any further IP if any of the discontinuation criteria listed in Section 7.1 apply.

Treatment after final overall survival data cut-off

At the time of the final DCO, the analysis portion of the clinical study will have been completed and all patients remaining in the study will be considered to have completed the analysis portion of the study. At the time of final DCO, the clinical study database will be closed to new data.

Patients in OS follow-up (progressed and have discontinued treatment) will be considered to have completed the study.

Patients who are receiving treatment at the time of final DCO may continue receiving IP if the Investigator judges that they are gaining clinical benefit.

All patients will receive scans and follow-up care in accordance with standard local clinical practice. All data will be recorded on patient charts but will not otherwise be reported for the purposes of this study.

For patients who do continue to receive IP beyond the time of the final DCO, Investigators will report SAEs to AstraZeneca Patient Safety via paper case report forms (CRFs) until 90 days after the last dose of study drug, in accordance with Section 8.4.1. Any SAE or non-serious AE ongoing at the time of the DCO is to be followed up at the discretion of the Investigator and per local practice and in alignment with the Dosing Modification and Toxicity Management Guidelines (Section 8.4.5), unless the event is considered by the Investigator to be unlikely to resolve, or the patient is lost to follow-up. Data will not be captured for the purposes of this study outside of being recorded in the patients' source documents.

Following the DCO, SAE reporting applies only to patients who are active on IP and within 90 days after the last dose; in all other cases, only a Statement of Death notification is to be sent to AstraZeneca.

Different drug supply options will be available depending on the country, and these will be proposed to the patient when the most appropriate alternatives for continued treatment have been agreed between AZ and the investigator. Options may include the participation in a new rollover study or, if the study drug has been locally approved for use in this disease indication, patients may be discontinued and switched to the marketed product, in accordance with local laws.

In the event that a rollover or safety extension study is available at the end of 24 months of study treatment, or at the time of the final DCO / database closure, patients currently receiving

treatment with durvalumab may be transitioned to such a study, and the current study would reach its end. The rollover or safety extension study would ensure treatment continuation with visit assessments per its protocol. Any patient who would be proposed to move to such a study would be given a new ICF.

